### **Model Checking and Diagnostics**

For the Repeated Measures Analysis (RMA) Model assumptions will be checked, and appropriate adjustments may be applied based on the data.

Distribution assumptions underlying the model used for analysis will be examined by obtaining a normal probability plot of the residual and a plot of the residuals versus the fitted values (i.e., checking the normality assumption and constant variance assumption of the model respectively) to gain confidence that the model assumptions are reasonable.

Non-parametric analyses, Mann-Whitney U (or Wilcoxon Rank-Sum) Test will be conducted if the normality assumptions do not hold.

### **Results presentation**

Presentation of results from a statistical analysis model will include the estimated mean treatment effects (Least Square Means (LSMeans)) and estimated mean treatment differences will be presented together with two-sided 95% confidence intervals standard error for mean difference and p-value.

### **Additional analysis**

#### **Summary analysis method**

To compare difference between baseline to Week 4, Week 8, Week 16, Week 24, Week 32, Week 42 and Week 52, a paired t-test will be used for primary endpoint change from baseline Multiple Sclerosis Quality of Life (MSQOL)-54 Composite scores to check the statistical significance.

To further evaluate if the improvements are clinically relevant, effect size of the treatment difference at Week 4, Week 8, Week 16, Week 24, Week 32, Week 42 and Week 52 will also be calculated for the efficacy endpoint using Cohen's d calculation. Cohen's d is a standardized measure of effect size (ES) that provides information on the amount of change in the outcome measure relative to the variation within the measure. Cohen's d is calculated as the difference between the HB-adMSCs mean score and Placebo mean scores divided by the standard deviations of the scores. An absolute effect size of <0.2 will be considered trivial,  $\geq 0.2$  as small,  $\geq 0.5$  as medium and  $>0.8$  as large .

Cohen's d = 
$$\frac{M_1 - M_2}{(sd_1 + sd_2)/2}$$
, where M1 and M2 are the Mean scores for HB-adMSCs and Placebo respectively, and SD1 and SD2 are the corresponding standard deviations.

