7. Visually confirm temperature tape is in biohazard bag and is within range (2° - 8° C), document compliance.
8. Visually confirm syringe is closed with cap.
9. Remove syringe from bag and begin mixing syringe, gently rocking back and as well as rolling between hands, bringing the study treatment to room temp, and suspending them into a homogenous solution. No particulates should be visible.
10. Inject the contents into a 250cc bag of normal saline for injection
11. Properly label the infusion bag with the subject ID, D.O.B, preparation date, time and expiration and cover it with an amber bag.

Once, the study treatment has been mixed by the unblinded pharmacist following the above procedures, the infusion nurse or designated study staff will administer the study treatment as follows:

1. Confirm that the subject number and DOB placed on the amber bag label belong to the subject receiving the infusion.
2. Administer the infusion solution over a period of 1h (infusion rate 4-5ml/min).
3. Do not store or reuse any unused portion of the infusion solution. Any unused product or waste material should be disposed in a biohazard container.
4. Complete the source documents of the visit to accurately collect the start and end times of the infusion and add comments if necessary.
5. The study's subject will be monitored for a total of 2 hours from drug exposure to discharge.
 - During the Investigational product administration (1 hour) vital signs will be measured at minute 0, 15, 30, 45, and 60.
 - Post infusion, vital signs will be measured at minute 90 and 120.
6. Follow study procedures as described in the schedule of assessments of the visit.

Investigational Product Assignment (Randomization and Blinding)

A total of 24 eligible subjects will be randomized to either placebo (approx. 12) or active drug (approx. 12) (HB-adMSCs) in a 1:1 balanced design. The randomization will be applicable only to eligible subjects. If a subject is not eligible during the screening process for study participation, this subject shall not be randomized to any group.

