### 3. STATISTICAL HYPOTHESES

The primary analysis will test whether HB-adMSCs is superior to Placebo according to the following statistical hypotheses:

**Null hypothesis H0:** The difference in change from baseline at Weeks 52 in Multiple Sclerosis Quality of Life (MSQOL)-54 Instrument scores between treatment groups (HB-adMSCs – Placebo) is equal to zero.

**Alternative hypothesis H1:** The difference in change from baseline at Weeks 52 in Multiple Sclerosis Quality of Life (MSQOL)-54 Instrument scores between treatment groups (HB-adMSCs – Placebo) is not equal to zero.

Secondary analysis will be tested for mean difference for change from Baseline to Week 52 for efficacy endpoints for both treatment groups,

**Null hypothesis H0:**  $\Delta = 0$

**Alternative hypothesis H1:**  $\Delta \neq 0$

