## 4. ANALYSIS SETS

Population	Definition / Criteria	Analyses Evaluated
Safety analysis set	

• All randomised subjects who received at least one dose of HB-adMSCs infusion or placebo.

• If participants receive a treatment different to their randomized treatment, they will be analysed according to the treatment actually received.

	

• Safety

• Study Population

Efficacy analysis set	

• All randomized participants who received all 6 infusions of HB-adMSCs or placebo.

• Participants will be analysed according to their randomized treatment.

	

• Efficacy

Screened Population	

• This population consists of all subjects who signed an ICF to participate in the clinical trial.

• This population will be used for summarizing screening failures and reasons for screening failures.

	

• Study Population

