#### 5.1.1. General Methodology

Unless otherwise stated, all hypotheses will be tested at a 2-sided significance level of 0.05 and 95% confidence interval. All continuous measurements will be summarised descriptively at each visit by treatment using observed data.

Summary of continuous variables will be presented using N, Mean, 95% confidence interval of mean, Standard Error of mean (SE), Standard Deviation (SD), Median and Range (Minimum and Maximum). The categorical variables will be presented using number and percentage based on N.

For measurements over time mean values will be plotted to explore the trajectory over time. Observed data will be used as the basis for plotting data along with bars as +/- SE, not otherwise specified.

As a primary analysis, a standard Analysis of Covariance (ANCOVA) will be applied for primary and secondary endpoint to test the significance of the effects of the treatment at Week 52. The model includes treatment as fixed factor and the corresponding baseline value as a covariate.

A parametric Repeated Measures Analysis (RMA) Model will be applied as a secondary analysis to test the significance of the effects of the treatment at Week 4, Week 8, Week 16, Week 24, Week 32, Week 42 and Week 52 including baseline as covariate.

Presentation of results from a statistical analysis model will include the estimated mean treatment effects (Least Square Means (LSMeans)). For all endpoints analysed statistically, estimated mean treatment differences will be presented together with two-sided 95% confidence intervals and p-values,

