#### HB-adMSCs - Placebo

Pairwise t-test will be performed on the efficacy endpoints to test the difference between baseline and week 52 (EOS) as secondary analysis. Data for all the efficacy outcomes will be checked for normality (Shapiro-Wilk Test). When there is a larger deviation of data distribution from normality, appropriate non-parametric test will be used.

Additionally, RMA and ANCOVA in a Bayesian framework using a non-informative prior will be conducted to estimate the posterior distribution and to estimate the probability that the true treatment difference of change from baseline to Week 4, Week 8, Week 16, Week 24, Week 32, Week 42 and Week 52.

Study population analyses including analyses of subject disposition, demographic and baseline characteristics, medical history, prior and concomitant medications.

Disposition summary includes, subject screened, randomized and disposition at end of study – Week 52 along with reasons for withdrawals. Subjects in different analysis populations also will be presented.

The screen failure table includes total number of screened subjects and reasons. The percentage in the screen failure table will be calculated based on total number of screened subjects as denominator.

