### **Results presentation**

Secondary endpoints will be summarized using n, mean, confidence interval of mean, SD, median, minimum and maximum. And p-value for paired comparison will be displayed for all post-baseline visits.

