### **6. SAMPLE SIZE DETERMINATION**

Sample size consists of up to 24 subjects who have been diagnosed with Relapsing Remitting Multiple Sclerosis.

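### Paired baseline-to-visit tests with displayed p-values, read naturally as within-arm, do not address HB-adMSCs versus placebo and should become descriptive only

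*SAP*

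**What the plan says.** SAP 5.2.2, under Additional analysis, states that "a paired t-test will be used for primary endpoint change from baseline" in the MSQOL-54 composite scores. It lists seven weeks from 4 to 52, and the stated aim is to check statistical significance. A signed-rank test is the fallback if normality fails. The results paragraph that follows says that the "p-value for paired comparison will be displayed for all post-baseline visits". SAP 5.3.1 repeats the paired tests for EDSS, Barthel Index, 9-Hole Peg Test and PHQ-9.

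SAP 5.1.1 gives the last visit a higher rank: "Pairwise t-test will be performed on the efficacy endpoints to test the difference between baseline and week 52 (EOS) as secondary analysis". SAP Section 3 says: "Secondary analysis will be tested for mean difference for change from Baseline to Week 52 for efficacy endpoints for both treatment groups". It then states a null of delta equal to zero without defining delta.

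The Holm procedure in SAP 3.1 is assigned to the secondary efficacy endpoints. It does not say that it covers paired tests on the primary endpoint, nor which tests on the secondary endpoints make up its family. The Protocol's Statistical Methods section promises a correction for post-hoc comparisons but names no method.

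The primary analysis is a between-arm ANCOVA at Week 52, and a between-arm repeated measures model supports it (SAP 5.1.1 and 5.2.2).

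**The concern.** The trial asks whether HB-adMSCs does better than placebo. A test of baseline against a later visit inside one arm does not answer that. The change also contains placebo response, regression to the mean and, for a task such as the 9-Hole Peg Test, practice. If one arm's p-value falls below 0.05 and the other's does not, that is not a test of the difference between them. Yet a table with a p-value for each arm at each visit invites that reading, and nothing in the SAP warns against it.

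With small arms the pattern can arise readily when both arms improve equally, because each arm's test has middling power. What is at stake is how the results are reported and understood, especially if the between-arm result is not significant.

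**Working it through.** The plan states no error rate for these tests and no power calculation, so there is no figure to reproduce.

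**Inputs from the documents**
- Level: "all hypotheses will be tested at a 2-sided significance level of 0.05 and 95% confidence interval" (SAP 5.1.1), unless otherwise stated.
- Size: "Sample size consists of up to 24 subjects" (SAP Section 6), allocated 1:1 with about 12 per arm (Protocol, randomisation section).
- Efficacy set: "All randomized participants who received all 6 infusions of HB-adMSCs or placebo" (SAP Section 4). Twelve per arm is therefore the expected maximum; 10 per arm is used as an assumed sensitivity value.
- MSQOL-54 after baseline: Weeks 8, 24, 42 and 52 only (Protocol Table 4). The SAP lists 2 composites x 2 arms x 7 weeks = 28 paired p-values; 2 x 2 x 4 = 16 of them can have data.

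**Assumption.** Both arms have the same true mean improvement, d, in units of the SD of the change score. The documents give neither an SD nor an expected placebo change, so d is shown over a range.

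**Formula for one test.** The paired t statistic has n - 1 degrees of freedom and noncentrality d x sqrt(n). Let p be the probability that it shows significant improvement at two-sided 0.05. The arms are independent, so:

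P(significant improvement on HB-adMSCs, not on placebo) = p x (1 - p)

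| d (SD of change) | p, n = 12 | p(1 - p), n = 12 | p(1 - p), n = 10 |
|---|---|---|---|
| 0 | 0.025 | 2.4% | 2.4% |
| 0.2 | 0.092 | 8.4% | 7.5% |
| 0.3 | 0.156 | 13.2% | 11.6% |
| 0.5 | 0.353 | 22.8% | 20.7% |
| 0.6 | 0.475 | 24.9% | 23.9% |
| 0.8 | 0.714 | 20.4% | 23.6% |
| 1.0 | 0.883 | 10.3% | 15.8% |

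The product cannot exceed 0.5 x 0.5 = 25%, which it approaches near d = 0.6 when n = 12.

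**Comparator.** A between-arm test at two-sided 0.05 gives a false claim for HB-adMSCs in 0.05 / 2 = 2.5% of trials per composite at Week 52. This does not depend on d.

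**Several tests.** A simulation of 20,000 trials used n = 12, 4 visits x 2 composites, and between-visit and between-composite correlations of both 0.7 or both 0.5 (assumed). At least one result significant on HB-adMSCs only appeared in 11-14% of trials at d = 0, 29-37% at 0.2 and 60-71% at 0.5. Unadjusted between-arm t-tests on change, over the same eight comparisons, gave at least one false claim for HB-adMSCs in 11-14% whatever d was. With no shared change the two approaches are therefore equally exposed. Only the paired approach gets worse as a shared change appears.

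**The case against.** The strongest reply is that the SAP's inference is already between arms. The primary hypothesis, the ANCOVA, the repeated measures contrasts and Cohen's d all compare HB-adMSCs with placebo, and no passage makes a within-arm p-value a criterion for efficacy. That stands. A reader might infer that the primary type I error is inflated; it is not.

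Other stronger readings are tempting and also go too far:
- **Every-visit tests as secondary analyses.** SAP 5.1.1 gives that label only to Week 52; the others are additional.
- **Within-arm as a stated fact.** The paired-test text does not say it. It is the natural reading of a baseline-to-visit test beside summaries by treatment. Likewise, the sentence promising p-values at each visit opens by naming secondary endpoints. It covers MSQOL-54 by its place in 5.2.2.
- **Section 3 as a within-arm null.** The wording allows this, but it follows a between-arm primary hypothesis and delta is undefined. It is ambiguous.
- **All paired tests outside Holm.** Coverage is not stated for the primary endpoint and is unclear for the secondary endpoints.
- **A pattern that is always frequent.** With no shared change it is 2.4% per test.

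A last objection concerns the remedy. A 95% confidence interval for an arm's mean change excludes zero exactly when its paired t-test gives p < 0.05, so removing p-values alone leaves the same temptation. That is correct, and the fix needs an explicit rule on interpretation.

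**Conclusion.** The concern holds as a matter of interpretation and reporting. The plan attaches formal p-values to comparisons that cannot separate treatment from whatever else changes over a year, and it raises one of them to secondary status. The wording of Section 3 adds to the confusion.

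The size depends on a change shared by both arms. Per test, with 12 per arm, the misleading pattern ranges from about the between-arm false-claim rate when there is no shared change to ten times that rate at worst (25% against 2.5%), then falls as both arms' tests gain power. The figures rest on equal true change and independent arms. The eight-test figures also rest on assumed correlations. The change is a cheap improvement to the SAP and does not correct any error in the primary test.

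**What to change.** 1. In SAP 5.1.1, 5.2.2 and 5.3.1, remove the paired t-test and signed-rank p-values, and the secondary label on the Week 52 paired test.
2. Show within-arm mean change with its 95% CI, marked as descriptive only.
3. In SAP Section 3, define delta as the HB-adMSCs minus placebo difference in change from baseline at Week 52, tested by the between-arm model contrast already planned. SAP 5.1.1 and 5.3.1 disagree on whether ANCOVA or the repeated measures model comes first for the secondary endpoints, so name the one that applies.
4. State that efficacy conclusions rest only on between-arm contrasts, and that one arm's interval or p-value is not to be compared with the other's.

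The cost is SAP wording and table shells. No new data are needed, and the planned summaries already include the mean and its confidence interval. What is lost is the within-arm p-values.

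### Clinical relevance is to be read from size bands on an unadjusted Cohen's d with no specified interval; at about 12 per arm the bands cannot support that reading

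*SAP*

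**What the plan says.** SAP 5.2.2, under Additional analysis (Summary analysis method), gives the purpose of the effect size: "To further evaluate if the improvements are clinically relevant, effect size of the treatment difference". The definition is "d is calculated as the difference between the HB-adMSCs mean score and Placebo mean scores divided by the standard deviations of the scores". The displayed formula is M1 - M2 over (sd1 + sd2)/2, "where M1 and M2 are the Mean scores for HB-adMSCs and Placebo respectively". The size labels use the absolute value: "An absolute effect size of <0.2 will be considered trivial", with small from 0.2, medium from 0.5 and large above 0.8.

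The results presentation for this analysis reads "Secondary endpoints will be summarized using n, mean, confidence interval of mean, SD, median, minimum and maximum", plus a paired p-value. It lists no interval for d. SAP 5.3.1 applies the same calculation to EDSS, Barthel Index, 9-Hole Peg Test and PHQ-9.

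On sample size, the protocol has 24 subjects "randomized to either placebo (approx. 12) or active drug (approx. 12) (HB-adMSCs) in a 1:1 balanced design". SAP section 6 says only "Sample size consists of up to 24 subjects who have been diagnosed with Relapsing Remitting Multiple Sclerosis". The efficacy set is "All randomized participants who received all 6 infusions of HB-adMSCs or placebo", so 12 per arm is about the most that can be expected.

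**The concern.** Three features combine here.

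- **A point estimate is graded without its uncertainty.** With two arms of about 12, d is very imprecise, and a label of medium or large hides that. The SAP states no other yardstick for clinical relevance, such as a minimal important difference for MSQOL-54.
- **d and the primary analysis estimate the difference differently.** The ANCOVA in 5.2.2 adjusts for baseline; d uses plain arm means. Chance baseline imbalance therefore affects the two differently, and they can disagree on size or sign.
- **The input is not defined.** The text does not say whether the mean scores are the values at the visit or the changes from baseline. The two give different numerators and different SDs.

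At stake is the wording of the study report. A chance difference could be described as a medium or large effect in a section whose stated purpose is to assess clinical relevance.

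**Working it through.** The documents give no power, SD, target effect or operating characteristic for d, so there is no planned figure to reproduce. The properties of the stated rule can be derived directly.

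**Inputs from the documents.** n = 12 per arm (protocol, randomization section); cut-offs 0.2, 0.5 and 0.8; denominator (sd1 + sd2)/2 (SAP 5.2.2).

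**Assumptions.** Normal data; equal SDs unless stated; baseline to follow-up correlation r of 0.5 to 0.8, because the documents give none.

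**1. How often chance alone reaches each band.** With no effect and a pooled SD, d = t × sqrt(2/n) with 2n - 2 = 22 degrees of freedom, and sqrt(2/12) = 0.408. So P(|d| ≥ c) = P(|t22| ≥ c/0.408).

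| Cut-off | Exact t, pooled SD | SAP formula, simulated | SAP formula, favouring HB-adMSCs only |
|---|---|---|---|
| 0.2 | 62.9% | 63.4% | 31.8% |
| 0.5 | 23.4% | 24.0% | 12.0% |
| 0.8 | 6.3% | 6.5% | 3.2% |

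With fewer six-infusion completers, the chance of |d| ≥ 0.2 under the SAP formula rises to about 66% at 10 per arm and 70% at 8. At 12 per arm with an SD ratio of 1.5 to 2 it is 64-65%. These rates are the same for visit scores and for changes.

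**2. Precision of d.** SE ≈ sqrt(2/n + d²/(4n)). At d = 0.5: sqrt(0.1667 + 0.0052) = 0.415, and 1.96 × 0.415 = 0.81, so the 95% interval is -0.31 to 1.31. At d = 0.2 it is -0.60 to 1.00; at d = 0.8 it is -0.03 to 1.63. An estimate on the medium threshold is compatible with anything from a small effect in the wrong direction to a large benefit.

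**3. Sign agreement with a baseline-adjusted difference, no true effect.** With the slope treated as known, the correlation between the unadjusted and adjusted differences is sqrt(1 - r²) for visit scores and sqrt((1 + r)/2) for changes. The chance of opposite signs is arccos(correlation)/π.

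- Visit scores: r = 0.5 gives arccos(0.866)/π = 16.7%; r = 0.8 gives arccos(0.600)/π = 29.5%.
- Changes: r = 0.5 gives 16.7%; r = 0.8 gives arccos(0.949)/π = 10.2%.

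Simulation with the slope estimated by ANCOVA at 12 per arm gives 16-30% for visit scores and about 11-17% for changes. The model checked had treatment and baseline only, without the stratification factors.

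**4. Denominator.** With equal arms and SD ratio k, the average SD is below the root-mean-square SD by the factor ((1 + k)/2)/sqrt((1 + k²)/2). |d| is then larger by 2% at k = 1.5, 5% at k = 2 and 12% at k = 3. With unequal arms it can go the other way. For 12 and 9 subjects with SDs 1.0 and 1.5, the pooled SD is sqrt((11 × 1 + 8 × 2.25)/19) = 1.235, against an average of 1.25.

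**5. Effect of adjusting.** Take the adjusted difference over the pooled baseline SD, times the small-sample factor 1 - 3/(4 × 22 - 1) = 0.966. Under the null it reaches 0.2 in about 57%, 49% and 42% of trials for r = 0.5, 0.7 and 0.8. It reaches 0.5 in about 17%, 10% and 5%, against 23% unadjusted.

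**The case against.** The strongest reply is that this is a descriptive additional analysis. It sits below the primary ANCOVA and the repeated-measures model, both of which report an adjusted difference with a 95% interval and p-value. No hypothesis test or multiplicity step depends on d. That is right and limits the importance of the point. The programming specification, which was not available, might also add an interval for d.

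Several stronger readings are tempting, and the documents do not support them:

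- **That the 63% is caused by the missing adjustment, the averaged SD or the missing interval.** It comes from the small sample and the 0.2 cut-off. Pooling the SD moves it by about half a point, an interval does not change it, and adjustment lowers it only to 42-57% under the assumed correlations.
- **That 63% of null comparisons would be called beneficial.** The bands count both directions; apparent benefit is about 32%.
- **That the SAP equates small with clinically relevant.** It links d to clinical relevance but names no band as the threshold.
- **That d has no direction.** The formula is signed, HB-adMSCs minus Placebo; only the label drops the sign. What is missing is a statement for each scale. A positive difference is favourable on MSQOL-54 and Barthel but unfavourable on EDSS.
- **That d conflicts in sign with the ANCOVA in up to 30% of null trials whatever the input.** That needs visit scores. The SAP also describes d in terms of the amount of change and refers to the efficacy endpoint, which is a change from baseline, so the lower range of about 11-17% is equally plausible.
- **That the averaged SD always inflates d.** With unequal arms it can deflate it. The formula is disclosed, and the effect at plausible SD ratios is minor.

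**Conclusion.** The point holds as a reporting defect. The SAP assesses clinical relevance by banding the point estimate of |d|, calculated from unadjusted arm means, with no interval specified and the input score undefined. At the planned size the bands largely reflect sampling noise. That result rests on normal data and on no more than about 12 per arm; fewer completers make it worse. The sign-disagreement figures rest in addition on the assumed baseline correlations and on which score is meant.

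The primary inference is unaffected, and the averaged-SD denominator is a minor matter. This is a cheap improvement, not a threat to the trial's main conclusion.

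**What to change.** In SAP 5.2.2, and by reference in 5.3.1:

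1. Define the effect size as the LS-mean difference from the model already specified, divided by a named SD, for example the pooled baseline SD. This removes both the visit-or-change ambiguity and the mismatch with the ANCOVA. A small-sample factor (0.966 at 22 degrees of freedom) may be added.
2. Report it with a 95% confidence interval.
3. State for each scale which sign favours HB-adMSCs.
4. Do not use the size bands to conclude clinical relevance. If relevance is to be judged, prespecify a threshold on the scale itself with its justification; otherwise drop the phrase.

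Adjustment and an interval do not remove chance labels: null medium labels fall only to about 5-17% under the assumed correlations. Item 4 is therefore needed as well.

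The cost is a short SAP edit and a small code change, with no new data. The reported effect sizes will carry wide intervals and may be smaller or larger than the unadjusted d.
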